## **Optimal postoperative chest tube and pain management in patients surgically treated for primary spontaneous pneumothorax; a randomized controlled trial.**

### **Summary**

**Rationale:** Guidelines lack high quality evidence on optimal postoperative chest tube and pain management after surgery for primary spontaneous pneumothorax (PSP). This results in great variability in postoperative care and length of hospital stay (LOS). Chest tube and pain management are prominent factors regarding enhanced recovery after thoracic surgery, and in standardised care they are crucial to improve quality of recovery and decrease LOS. We hypothesize that early chest tube removal accompanied by a single-shot paravertebral blockade (PVB) for analgesia is safe regarding pneumothorax recurrence and non-inferior regarding pain, but superior regarding LOS when compared to standard conservative treatment.

**Objective:** Our objective is to compare the efficacy of early chest tube removal combined with single-shot PVB versus standard treatment (chest tube for at least 3 days and thoracic epidural analgesia (TEA)) after surgery for PSP.

**Study design:** Multicentre four-arm randomized trial, 2x2 factorial design

**Study population:** Patients  $\geq 16$  years with PSP referred for surgery.

**Intervention:** 1) Early chest tube removal when the following postoperative criteria are met: no air leakage for at least 4 hours, complete lung expansion on postoperative X-ray, absence of bloody drainage. 2) Intraoperative single-shot PVB (level T2-T11) with a local anaesthetic for analgesia.

**Main study parameters/endpoints:** Recurrence of pneumothorax as safety measure, proportion of pain scores  $\geq 4$  on a numerical rating scale of 0-10, and LOS

**Nature and extent of the burden and risks associated with participation, benefit and group relatedness:** There will be negligible risks to participation since the intervention strategies are already in use in some Dutch centres and have been demonstrated feasible and safe in single centre studies. The additional burden for the participants will be the completion of questionnaires.

## 1. INTRODUCTION AND RATIONALE

Primary spontaneous pneumothorax (PSP) is common and mostly occurs in young and healthy males with a reported incidence rate of 12.3 per 100,000 (1). Treatment is primarily conservative, but guidelines recommend pleurodesis through video-assisted thoracoscopic surgery (VATS) in case of recurrent PSP or persistent air leak (i.e.  $\geq 5$  days)(2,3).

Recommendations on postoperative chest tube policy and type of analgesia are however lacking. Historically, postoperative chest tubes are put on suction and left in place for at least 3 days, irrespective of absence of air leakage. This period was deemed necessary for adequate pleurodesis and prevention of recurrence. A recent review demonstrated that different chest tube protocols were used among several studies and that LOS was directly influenced by chest tube duration(4). This study reported that chest tube removal as early as postoperative day (POD) 2 is safe. Also, Furuya showed that chest tube removal, even on the same day of surgery, is safe and feasible (5). Next to chest tube duration, one randomised trial compared suction versus water seal after video-assisted thoracoscopic surgery (VATS) in PSP (6), demonstrating water seal to result in faster chest tube removal and shorter LOS. A meta-analysis of randomised trials further showed no advantage of chest tube suction after pulmonary surgery in general (7). However, due to lack of high quality evidence and recommendations in guidelines, great variability is induced because decisions on the chosen approach for chest tube management is mainly based on personal preferences (8). A national survey among Dutch thoracic surgeons demonstrated that 31% removed the chest tube early in case of absence of air leakage and 69% kept the chest tube in place for at least a few days ranging from 2 – 5 days (9). However, according to the guideline by the Dutch Association of Chest Physicians (NVALT), early chest tube removal is associated with less pain, more rapid mobilisation, lower risk of postoperative infection and shorter LOS (10).

In addition to the absence of high quality evidence on chest tube policy, there is also a lack of unambiguity regarding pain management after surgical treatment of PSP. Although

thoracic epidural analgesia (TEA) is considered the gold standard for pain management after thoracic surgery, the use of VATS increases the interest in locoregional analgesia(11,12). The guideline on enhanced recovery after thoracic surgery (ERATS) suggests using locoregional analgesia to enhance mobilization and patient satisfaction, whereas the more recent PROSPECT guideline even recommends paravertebral blockade (PVB) as locoregional analgesic instead of TEA (12,13). The arguments are that locoregional analgesia provides sufficient analgesia without epidural related side-effects, e.g. hypotension, immobilization and urinary retention (14). In particular, PVB has shown to have a comparable analgesic effect as TEA (15,16) and plays an important role in thoracic fast-track surgery (17). Also, Xie compared PVB versus TEA versus no block in children after pleurodesis for spontaneous pneumothorax and showed that all groups had good pain control with pain scores < 4 (18). However, the earlier mentioned national survey among Dutch thoracic surgeons showed TEA to be still the most applied (78%) analgesic technique after VATS for PSP (9).

Both chest tube and pain management after surgery for PSP have been addressed by the Dutch Society of Lung Surgery (NVvL) as their knowledge gap with highest priority. The objectives of our study therefore are to compare early chest tube removal versus standard drainage for at least 3 days, and to compare the use of TEA versus PVB in patients who undergo VATS pleurodesis for PSP. We hypothesize that early chest tube removal accompanied with a single-shot PVB is safe regarding recurrence rate and non-inferior regarding pain, but superior regarding LOS compared with the current standard treatment.

## 2. OBJECTIVES

Our primary objective is to compare the efficacy of early postoperative chest tube removal and single-shot PVB to usual care which comprises late chest tube removal and TEA, in patients surgically treated for PSP. Efficacy is defined as proving safety regarding recurrence and non-inferiority regarding pain, and superiority regarding LOS.

[figure not shown]
Our secondary objectives are quality of recovery (QoR), quality of life (QoL), duration of chest tube drainage, additional opioid use, postoperative morbidity, mobilization, health status, and cost-effectiveness and –utility.

## 3. STUDY DESIGN

A multicenter four-arm randomized trial (2x2 factorial design) comparing early postoperative chest tube removal and standard chest tube removal (after at least 3 days), as well as comparing TEA and PVB as postoperative analgesic techniques in patients with PSP undergoing VATS. This design allows independent analysis of chest tube and pain management. Early versus late chest tube removal will be compared on safety regarding recurrence and TEA will be compared with PVB on pain (non-inferiority). We hypothesize that both early chest tube removal and PVB will lead to a shorter LOS (superiority).

Since current clinical evidence does not point out which pleural intervention is superior regarding morbidity and risk of recurrence, the type of chosen surgery will be at the discretion of the hospital in which patients are being treated: either total pleurectomy or total chemical pleurodesis with talc. Randomisation will be stratified to age in which 40 years is the cut-off point and to type of centre regarding surgery (either pleurectomy or chemical pleurodesis). The CONSORT 2010 flow diagram is shown in Figure 1.

Figure 1 CONSORT 2010 Flow Diagram

### 3.1 Hypothesis

1. Early postoperative chest tube removal, at the earliest at 4 hours after surgery, is safe and does not lead to higher absolute recurrence rates compared to standard chest tube management.
2. Single-shot PVB is non-inferior to TEA regarding pain in patients undergoing VATS for PSP.
3. Provided that early chest tube removal is safe and single-shot PVB is non-inferior regarding pain, we expect that their combination is superior regarding LOS compared with current standard treatment, comprising late chest tube removal and TEA.

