The shortened LOS however is only acceptable in case recurrence rates are equal between the early and late chest tube removal groups (patients' perspective). Therefore, three interim analyses will be performed under supervision of a DSMB after 90, 180 and 270 patients who completed 30-day follow-up. When the incidence of recurrences after early chest tube removal exceeds the incidence after late tube removal by more than 9 cases, then early tube removal will no longer be applied and the study will continue with the two late tube removal subgroups, unless the DSMB advises otherwise. The maximum allowable skewness of 9 extra recurrences after early tube removal is based on the following considerations. First, pneumothorax is not directly life threatening and 9 recurrences extra give a modest maximum excess of 5.49% (9/164). Second, a higher excess incidence ( $\geq 10$ ) leads to a decrease in expected savings in LOS by well more than 20%, and undermines the economic benefit of early tube removal too much (164 early removals save 230 hospital days and  $\geq 10$  extra recurrences reduce this gain with a least 50 days).

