## 8. METHODS

### 8.1 Study parameters/endpoints

#### 8.1.1 Main study parameter/endpoint

As explained in the sample size section, we discussed the relevance and importance of several outcome measure with a patient panel. Although we expect the largest advantage of our interventions to be a shortened LOS with high impact on cost-effectiveness, the patient panel emphasized that short LOS is important but inferior to recurrence rate of pneumothorax. Next to recurrence rate, patients indicated acute postoperative pain to be an important topic as well. Lastly, patients emphasized uniformity in chest tube policy, the necessity of having a bladder catheter and uniformity in radiology assessments as important factors as well. Together with the patient panel we made the following ranking: 1) recurrence rate; 2) postoperative acute pain; 3) LOS; 4) uniformity in chest tube policy; 5) the need for a urinary catheter; and 6) uniformity in radiologic assessments (CT and X-ray). In addition, the reference panel of Patiëntenfederatie Nederland advised us during the subsidy application to include QoL as outcome parameter in our study.

Primary outcomes:

1. Safety outcome: absolute number of patients with recurrence (maximum allowable difference between early and late chest tube removal groups of 9 recurrences) defined as having an ipsilateral recurrent pneumothorax after chest tube removal, confirmed by X-ray or CT within 1-year, requiring reintervention (either tube thoracostomy or reoperation) or hospital readmission.
2. The primary outcome measure (non-inferiority) for our second intervention (single-shot PVB) will be the proportion of NRS  $\geq 4$ , defined as the number of NRS scores  $\geq 4$  divided by the total number of NRS measurements obtained during POD 0-3. A minimum of 11 NRS pain scores will be collected (1 at the recovery room, and 10 afterwards on the ward).
3. The primary outcome measure for our both interventions (early chest tube removal and single-shot PVB) will be LOS, defined as the total number of in-hospital days including readmissions due to complications or recurrence within 30 postoperative days. The day of surgery will be POD 0. Discharge criteria are: absence of chest tube, sufficient pain control (NRS $<4$ ) with oral pain medication, absence of fever ( $< 38.5$  °C) and being able of self-care.

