### **9.5 Data Safety Monitoring Board (DSMB)**

Based on our systematic review recurrences are expected to be equal in the early and late chest tube removal. However, our patient panel emphasized that a shorter LOS (primary outcome) should not be accompanied by a higher recurrence rate in the intervention group. Therefore, a DSMB will be established to perform ongoing safety surveillance and interim analyses on the safety data. This committee is independent and has no conflict of interest with the sponsor of the study. The DSMB will monitor the safety of this study regarding

recurrence rate for early and late chest tube removal. Three interim analysis will be performed after 90, 180 and 270 patients who completed 30-day follow-up. When the incidence of recurrences after early chest tube removal exceeds the incidence after late tube removal by more than 9 cases, then early tube removal will no longer be applied and the study will continue with the two late tube removal subgroups (only randomizing and analyzing for TEA vs PVB), unless the DSMB advises otherwise. The maximum allowable skewness of 9 extra recurrences after early tube removal is based on the following considerations. First, pneumothorax is not directly life threatening and 9 recurrences extra give a modest maximum excess of 5.49% (9/164 patients in the early tube removal group). Second, a higher excess incidence ( $\geq 10$ ) leads to a decrease in expected savings in LOS by well more than 20%, and undermines the economic benefit of early tube removal too much (164 early removals save 230 hospital days and  $\geq 10$  extra recurrences reduce this gain with a least 50 days).

The advice(s) of the DSMB will only be sent to the sponsor of the study. Should the sponsor decide not to fully implement the advice of the DSMB, the sponsor will send the advice to the reviewing METC, including a note to substantiate why (part of) the advice of the DSMB will not be followed.

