### 11.4 Benefits and risks assessment, group relatedness

According to a survey among Dutch thoracic surgeons early tube removal is used in 31% and late tube removal in 69% and regarding pain management TEA was used in 78% and locoregional techniques in 11% (9). The variability, also demonstrated in our literature review, confirms the lack of a standardized guideline. However, late tube removal and TEA are mostly performed and are seen as current standard of care.

To the best of our knowledge, the interventions, early tube removal and single shot PVB, do not expose participants to additional risks compared to late tube removal and TEA. The interventions are not experimental and already implemented in some hospitals (inter)nationally. Although we expect early recurrence rate to be equal regarding early and late tube removal, we appointed a DSMB to monitor the safety on this outcome since a higher recurrence rate in the intervention group is not accepted (as indicated by our patient advisory board). Benefits of early tube removal might be shorter LOS and higher patient satisfaction. Further, single shot PVB has a reduced risk of bleeding, nerve damage, insertion site infection, post puncture spinal headache and failure of the analgesic technique compared to TEA. Benefits are omitting epidural related side-effects, such as immobilisation, urinary catheter and hypotension. It is realistic to expect that patients with single shot PVB will have more episodes of NRS  $\geq 4$  and thus needing more morphine to control the pain.

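### The protocol requires recurrence after early chest tube removal to be equal or not higher, yet its primary safety outcome and stopping rule accept up to 9 extra recurrences, about a doubling of the expected rate

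*Protocol*

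**What the plan says.** Four places in the protocol set a standard of no excess:

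- **3.1 Hypothesis:** early removal "is safe and does not lead to higher absolute recurrence rates compared to standard chest tube management".
- **4.4, Chest tube management:** "The shortened LOS however is only acceptable in case recurrence rates are equal between the early and late chest tube removal groups".
- **9.5 DSMB:** the patient panel's view is that a shorter stay "should not be accompanied by a higher recurrence rate in the intervention group".
- **11.4 Benefits and risks:** "a higher recurrence rate in the intervention group is not accepted", attributed to the patient advisory board.

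The operational text sets a tolerance:

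- **8.1.1, primary outcome 1:** "maximum allowable difference between early and late chest tube removal groups of 9 recurrences".
- **4.4, repeated in 8.8 and 9.5:** the early arm is dropped, unless the DSMB advises otherwise, when its recurrence count "exceeds the incidence after late tube removal by more than 9 cases, then early tube removal will no longer be applied". Section 10.4 gives the same limit for the interim analyses.
- **4.4 and 9.5, justification:** "9 recurrences extra give a modest maximum excess of 5.49% (9/164"), together with the argument that 10 or more extra recurrences would use up too much of the saving in hospital days.

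Sections 4.4 and 9.5 each contain both standards. Hypothesis 2, on pain, is worded as non-inferiority and has a stated margin in 4.4. Hypothesis 1 is not worded that way.

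**The concern.** An excess of 9 recurrences is neither equal nor not higher, and no section defines those words in terms of the 9-case limit. A trial that ends with, say, 6 more recurrences after early removal meets the primary safety outcome in 8.1.1. The same result could be challenged under 11.4, and both readings have textual support.

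This matters for three reasons. Patients ranked recurrence first among the outcomes (8.1.1). Under hypothesis 3, the length-of-stay (LOS) claim for the combined strategy depends on early removal having been found safe. And 11.4 is the benefit-risk statement: it gives the strict standard without mentioning the tolerance. A statistical analysis plan cannot settle the matter, because the hypothesis, the tolerance and the ethics statement are all fixed in the protocol.

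The tolerance is given only as an absolute 5.49%. The protocol does not set it against the recurrence rate that it expects.

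**Working it through.** **Inputs.** 164 patients per tube group (4.4); tolerance of 9 extra recurrences (4.4, 8.1.1); pooled recurrence of 4.59% with early and 5.57% with late removal (5.3, Safety regarding chest tube management); LOS saving of 1.4 days per patient (4.4).

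**The plan's own figures reproduce.**

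- Tolerance: 9/164 = 5.49%.
- Days saved: 164 × 1.4 = 229.6, stated as 230.
- Loss from 10 or more extra recurrences: 50/229.6 = 21.8%, consistent with the statement that more than 20% would be lost.

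**Relative size of the tolerance.**

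- Expected late recurrences: 164 × 0.0557 = 9.13.
- With 9 more: 18.13, and 18.13/164 = 11.06%.
- Ratio: 18.13/9.13 = 1.99.

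**How often the limit is met when hypothesis 1 is false.** Let D be the early count minus the late count, with independent Bin(164, p_early) and Bin(164, 0.0557). P(D ≤ 9) is the exact sum over the two distributions. It treats the limit as one comparison at the end of the trial and ignores the interim looks.

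| True early rate | True excess | P(D ≤ 9) |
|---|---|---|
| 4.59% (review figure) | −0.98 points | 99.7% |
| 5.57% (equal) | 0 | 98.9% |
| 8.57% (assumed) | +3 points | 84% |
| 11.06% (assumed, a doubling) | +5.49 points | 54% |

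The first two rows use rates given in the protocol. The last two are assumptions, chosen to show what the limit does when early removal really is worse.

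**What an observed excess of exactly 9 would show.** Take 18/164 against 9/164:

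- Difference = 0.0549.
- SE = √(0.1098 × 0.8902/164 + 0.0549 × 0.9451/164) = 0.0302.
- 95% interval = 0.0549 ± 1.96 × 0.0302, or −0.4 to 11.4 percentage points.

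So a result at the limit does not show that the true excess is at most 5.49 points.

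**Could the trial test 5.49 points as a margin on true risk?** With both true rates at 5.57%:

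- SE = √(2 × 0.0557 × 0.9443/164) = 0.0253.
- Power at one-sided 0.025 = Φ(0.0549/0.0253 − 1.96) ≈ 58% (normal approximation).

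**The case against.** The strongest reply is that there is only one decision rule. Every operational section uses the limit of 9, and none declares early removal unsafe at an observed excess of 1. Hypothesis 1 is about true rates, and testing a directional hypothesis with a tolerance is ordinary. The sentences in 9.5 and 11.4 report what patients want and explain why a DSMB exists. In 4.4 the tolerance follows directly from the equality condition, is disclosed and is given two reasons. Whether 5.49% is modest is the sponsor's judgement.

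Much of this stands. There is one operational rule, it is openly stated, and its size is the sponsor's choice. But the reply does not remove the conflict of wording. Section 4.4 presents the tolerance as a consequence of requiring equal rates, and it is not one. Section 11.4 states the strict standard without the tolerance.

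Two stronger readings are tempting, and the documents support neither.

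- A reader might take the chance of an observed excess of 1 to 9 as the share of trials in which two rules disagree. By the same calculation that chance is 29% at the review's rates, 44% at equal rates and up to 67% at other true rates. Most of it is sampling noise: with identical true rates hypothesis 1 is true, and the limit passes 98.9% of trials. Values of 65 to 67% also need true early rates of about 7.6 to 8.6%, which the protocol does not give.
- A reader might treat the 9-case limit as a non-inferiority margin of 5.49 points on true 1-year risk. The protocol limits an observed count. An observed excess of 9 has an upper 95% limit near 11.4 points, and power for such a margin would be about 58%.

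**Conclusion.** The inconsistency is real. Sections 3.1, 4.4, 9.5 and 11.4 ask for equal or no higher recurrence, while 8.1.1 and the stopping rule accept an excess that takes the protocol's expected late rate from about 5.6% to 11.1%. Meeting the limit cannot establish that recurrence is not higher: it would be met in about 54% of trials under a true doubling and in about 84% under a true excess of 3 points. These probabilities assume 164 evaluable patients per group, a late rate of 5.57%, independent binomial counts and a single final comparison.

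The finding does not say that 9 is the wrong number, that the tolerance is concealed, or that a second decision rule exists. It also does not show that anyone will overstate the result; the protocol simply leaves that open. The correction should be made because the safety conclusion conditions the LOS claim.

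**What to change.** Amend the protocol so that 3.1, 4.4, 9.5 and 11.4 agree with the tolerance in 8.1.1. Either the wording or the tolerance can change; which excess is acceptable is for the sponsor to decide.

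- Beside the 5.49%, state its relative meaning: about 5.6% against 11.1% at the expected late rate.
- If the 9-case tolerance is kept, limit the permitted conclusion to an observed excess within the prespecified tolerance. Report it with the risk difference and its confidence interval. Do not describe the result as equal, as not higher, or as demonstrating a 5.49-point margin on true risk.
- Carry the same wording into the safety condition of hypothesis 3.

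The cost is an amendment to the text and a less favourable safety claim. No extra patients or data are needed for this. A formal test of a margin on true risk would be a different design, for which the present size gives about 58% power.

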## 4. STUDY POPULATION

### 4.1 Population

All patients from 16 years who are referred for surgery for PSP are eligible for this trial. This withholds PSP patients with (contralateral) recurrence, prolonged air leak (> 5 days) at initial occurrence of PSP, an accompanied hemothorax or a profession at high risk for pneumothorax such as aviation, diving, polar explorers or working with compressed air.

